Hypothesis 1b: Improvements in language achieved with combined tDCS-behavioral therapy but not behavioral therapy alone will persist at 2 weeks, 2 months and 6 months post-intervention. Hypothesis 1c: Stimulation of the propose areas during behavioral therapy will improve performance in other language and cognitive functions specific to the region of interest. Specifically, for SMG, improvements will be observed in spelling, naming, working memory and repetition; and for IFG and MTG, in spelling, naming, working memory, articulation, and syntactic comprehension. Hypothesis 1d: The therapeutic effect of tDCS will exhibit an interaction between hemisphere of stimulation (left vs. right) and stage of disease (early vs. middle), such that left hemisphere stimulation will be more effective at an early stage, whereas at later stages right hemisphere stimulation. Hypothesis 1e. Improvements in language achieved with combined IFG tDCS-behavioral therapy or sham and behavioral therapy alone will correlate with increases in daily physical activity and evening sleep efficiency and quality (using both self-report and objective measures) and there will be greater improvements in sleep efficiency and exercise in the tDCS condition as opposed to sham, because the area we target (left or right IFG) with 2x2 in electrodes incorporates premotor and motor areas that have

been found to improve the perceived difficulty and amount of exercise and sleep efficiency.

Hypothesis 1f: Beginning with a 3-week CBT treatment with tDCS over the DLPFC before beginning computerized cognitive/speech therapy at home will foster motivation and engagement in the consequent therapy by establishing routine, form, and helping manage psychological barriers to therapy beforehand.

**Primary Objective 2 (imaging):** To develop biomarkers for the effects of intervention using H-MRS. We will use H-MRS to detect NAA and GABA before, after and at follow-up intervals and evaluate the correlation between: (1) NAA/ GABA levels and (2) spelling, naming, and/or repetition accuracy of participants with PPA and MCI at each time point.

Hypothesis 2a: We hypothesize that tDCS coupled with behavioral therapy will result in enhanced, relative to behavioral therapy alone (with sham tDCS), levels of NAA at the stimulation sites where tDCS resulted in improved spelling relative to behavioral therapy alone.

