conditioning using tDCS have received Johns Hopkins IRB approval. We will use either the same equipment as [name] and his team have used (a Chattanooga lonto Device) as well as the same application technique, recently acquired state-of-the-art device using special software for doubleblinding (Soterix 1x1 CT: clinical trials), or a Neuroelectrics Starstim 8 device, which is a high-definition tDCS cap with higher precision. In order to administer intervention during the global pandemic and in a virtual manner, we will offer the option of remote stimulation (Soterix mini-CT device and MIND STIM+, YBrain). Attached please find letters from Clinical Engineering documenting that the tDCS devices have undergone clinical inspection as well as the manuals. When remote devices are implemented, participants and spouses will be trained prior to intervention and sessions will be conducted in real-time via video conference (e.g., Zoom). Stimulation will be delivered at an intensity of 1-2mA (estimated current density 0.04 mA/cm2; estimated total charge 0.048C/cm2) for a maximum of 20 minutes in the tDCS groups and for a maximum of 30 seconds in the Sham group. For both interventions (tDCS and Sham) the electrical current will be increased in a ramp-like fashion at the onset of the stimulation eliciting a transient tingling sensation on the scalp that usually disappears over seconds. Although the ramping process requires the researcher's input, it is now feasible to blind study staff who will be applying tDCS, as well as participants, as we now have a box that allows another member of the team to set the box to "tDCS" or "sham" without the knowledge of the researcher providing the therapy. In the Starstim 8 and remote devices, double-blinding is achieved through codes known only to the PI who is not administering any stimulation or evaluation, so both the technician or professional who administers the stimulation and evaluation are blind to the current condition being either actual tDCS or sham. After the ramping, in the sham condition, the intensity drops to 0 mA. These procedures have been shown to successfully blind participants as to whether they were members of experimental or control groups (Gandiga et al., 2006). The sites of tDCS application will be determined by the type of therapy used and the PPA variant group or MCI and will be either the inferior frontal gyrus (IFG), the supramarginal gyrus (SMG), or the middle temporal gyrus (MTG) or a combination as shown in the literature. A recent meta-analysis of the functional neuroimaging literature on spelling has not yet identified clearly the neural substrates for PG conversion; the most plausible network includes the inferior parietal lobule including the supramarginal gyrus (Purcell et al., 2011). This area has also been identified as a critical area for spelling in the lesion literature as well. Another plausible area that shows activations during both PG conversion and lexical (word) spelling is the inferior frontal gyrus (IFG) (Purcell et al., 2011) and lesions in the IFG are associated with impaired PG conversion (Beeson et al., 2010). The stimulation site of IFG will be determined between F7 and F8 electrodes and that of SMG between TP3 and TP4 using the EEG 10-20 electrode position system (Homan, 1988). Additionally, studies have reported positive results of tDCS over the left dorsolateral prefrontal cortex (DLPFC) leading to improvement in attention deficits due to stroke, Parkinson's disease, and major depression (Boggio et al., 2006, 2007; Fregni et al., 2006; Kang et al., 2009). In addition to improving attention, anodal tDCS at the left DLPFC has been shown to improve working memory in TBI patients (Ulam et al., 2015). We hypothesize that anodal tDCS over the L DLPFC when administered in combination with cognitive training will improve language performance of PPA and MCI participants more than behavioral therapy alone, and that improvements may generalize to some other cognitive functions. The dependent variable will be the same baseline and post-therapy evaluation as described above that will take place before, after, 2 weeks and 2 months post-stimulation for each stimulation condition (see Table 1). These same areas, predominantly on the left, are activated during naming (Jarso et al., 2013) and working memory (Philipose et al., 2007). In most cases of PPA and all cases of MCI, we will stimulate areas of the left hemisphere that are not atrophied. In the most advanced cases of PPA, with severe left hemisphere atrophy, we will stimulate the same sites in the right hemisphere in order to stimulate its compensatory mechanisms (see Hypothesis 1d). By this design we will be able to achieve a within-subject design for all conditions as well as to evaluate immediate, short- and long-term effects of each stimulation site without confounds and without any carry-over effects. We will also conduct a 6-month language evaluation to assess the overall therapy gains.

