#### Analyses

On careful consideration of the literature and consideration of the degenerative nature of the disease, its variability, and the poorly understood effects of tDCS we have selected a within-subject, cross-over design. This design is the one most commonly used in tDCS studies (below we discuss reasons for excluding a tDCS-only condition). Furthermore, in consultation with the 3 study team statisticians we evaluated whether this design would be appropriate given our preliminary data. As shown in preliminary study #1, the carry-over effect between the first period and the others is small and in this situation a cross-over design is recommended (Liang & Zeger, 1986). In the within-subject crossover protocol, each participant will be administered three experimental conditions: Control (natural progression), IFG tDCS+language (henceforth abbr. tDCS treatment) (word production) and sham tDCS+language (henceforth abbr. tDCS treatment) (word production) and sham tDCS+language (henceforth abbr. tDCS treatment). To achieve an accurate estimate of degeneration and rate of decline in each participant at their particular stage of the disease progression, each participant will first be enrolled in the control condition (natural progression). All analyses, behavioral and imaging, will be under the oversight of the study statisticians.

The genetic analysis will be done under the supervision of [name] and DNA samples will be provided by the Genetic Core facility at Johns Hopkins University. Based on previous research supporting that BDNF modulates tDCS outcome we will focus our analysis on the BDNF (/Val/Met polymorphism) and regulatory variants in closely functionally related genes. Final decisions will be made immediately before genotyping. To give an example, we may use the BDNF protein association network from the STRING functional protein association networks database (https://string-db.org/), a curated database providing valid expandable information on functional gene networks. Genetic variants that regulate these genes are

then identified from public gene expression databases such as GTEx (https://gtexportal.org), which report variants whose genotype correlates strongly with gene expression across tissue types, i.e. they are expression quantitative trait loci – eQTLS).

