## b. Study duration and number of study visits required of research participants.

Before any intervention participants will be enrolled in a control condition for 12 weeks during which no therapy will be provided to enable us to assess their personal decline rate. After this period they will be randomly assigned to either sham or tDCS experimental conditions. Three pre-training sessions may be proposed to test the tDCS experimental conditions before training. After 1-3 weeks of tDCS application (3-5 sessions in a week, 5-15 sessions per stimulation site) there will be an interval of approximately 2 months and then we will implement the other two tDCS conditions in a within-subject cross-over design, an example of which is shown in Table1. We will follow-up the participants with 2-week, 2-month and a final 6-month follow-up sessions. For those participants who are long-distance, at the 2-week time point we may use a video conferencing tool such as GoToMeeting to administer the assessments. This is to mitigate the costs of travel for a short appointment. In these sessions we will administer the behavioral therapy assessment as described in the therapy section. We will test participants with both the practiced items and unpracticed items to look at generalization effects to untrained items. Given that we will test each participant in different conditions, an example of the sequence of conditions is shown in Table 1. After the final evaluation of interventions, we will offer an optional remote extension phase. This will consist of 18 additional months of intervention: 50 therapy sessions+tDCS (in 10 weeks) every 3 approximately months for a 18-month period, depending on availability, using different areas of stimulation (either the IFG, SMG, MTG, or DLPFC or Precuneus based on previous literature, see above in tDCS methods for details) for up to 18 months in total. We will complete another full evaluation of language and cognitive skills at the end of the stimulation phase. We will compare maintenance of therapy gains for individuals who participate in these remote sessions to those who do not, to answer the question whether tDCS effects may be extended beyond the initial 2-month period follow-up, up to 18 months and whether the rate of decline may change. This is very important because long periods of interventions and followup are needed in studying intervention outcomes in a neurodegenerative disorder.

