Table 1: Timecourse of interventions (18 sessions) and evaluations for two groups of participants in the crossover design (W: Week, LIFG: left inferior frontal gyrus, LMTG: left middle temporal gyrus, LIPL: left inferior parietal gyrus; eval (b+a): evaluation before and after or evaluation only; 18: number of sessions).

Time	W1-12	W14-20	W22-24	W27	W233-35	W38	W44	W61
Group 1: control then sham then tDCS	Control	1 sham 1 LMTG 1 LIPL	15 sham	2 w eval	15 LIFG	2 w eval	2 m eval	6 m eval
Group 2: control then tDCS then sham	Control	1 sham 1 LMTG 1 LIPL	15 LIFG	2 w eval	15 sham	2 w eval	2 m eval	6 m eval

Both Groups eva	val (b+a) eval (b+a) eval (b+a)	Eval eval (b+a)	eval Eval	val
-----------------	---------------------------------	-----------------	-----------	-----

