## c. Statistical plan including sample size justification and interim data analysis.

Design. This is a crossover trial, where each participant will be randomly assigned to receive either "IFG tDCS, then sham then SMG (in case a second stimulation site is implemented)" (group1) or "SMG then sham then IFG" or "sham then IFG then SMG". In case a second stimulation site is not implemented participants will receive either sham and then tDCS (group 1) or tDCS and then sham (group 2). Based on previous studies regarding long-term effects of tDCS (see Fiori et al., 2011; Fridriksson et al., 2011; both looking at 3-weeks post-stimulation in participants with aphasia) and given the degenerative nature of PPA (and some cases of MCI), we assume that even though the effect of tDCS on the absolute level of the outcome may or may not persist at 2 weeks, the effect on the rate of decline persists no longer than 2 weeks. Analyses. The primary analyses will be a robust type of repeated measures Multivariate ANCOVA. Specifically, for each subject (i) and at follow-up times t=immediately after treatment, then 2 weeks and 2 months, we will consider the data  $IFG_{ti}$ ,  $SMG_{ti}$ , and  $S_{ti}$ ; here,  $IFG_{ti}$  is the change of outcome from just before IFG tDCS treatment to time t after IFG tDCS treatment for subject i; and similarly for SMGt,i, and St,i for IFG tDCS and sham. For the behavioral methods, change of outcome is considered the difference (before and after therapy) of the independent measure of initial letter-sound associations learned. Then the research hypothesis that IFG (or SMG) treatment is superior to sham will be tested by testing the hypotheses that the distribution  $pr(R_{ij} - S_{t,i})$  (or  $pr(L_{t,i} - S_{t,i})$ ) is not centered at zero. This will be done nonparametrically by obtaining the latter null distributions by the random permutation of the treatment labels (IFG, S, SMG) of the data for each patient (Rosenbaum, 1988). The design effect, i.e., the ratio of sample sizes needed by an independence design vs. the crossover design to achieve a given power, depends on the correlations of outcomes across times and treatments. We have calculated that this crossover design with 30 participants and design effect of 1.5 has power 75% to detect an effect size of 0.8 between a tDCS site and sham treatment. In secondary analysis, we will use regression to examine if any effects of tDCS vary across participants with different characteristics such as age and atrophy volume. The present design allows us to evaluate the language and neuromodulatory effects of both IFG and SMG stimulation as well as language therapy alone (in the condition of sham stimulation).

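### Six months after treatment, tDCS cannot be separated from therapy alone on outcomes shared by both crossover blocks (Hypothesis 1b), and the hemisphere-by-stage interaction (Hypothesis 1d) is not identified

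*Combined protocol and SAP*

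**What the plan says.** Primary Objective 1 asks whether tDCS improves language more efficiently and for longer than behavioral therapy alone. Hypothesis 1b makes this specific: "Improvements in language achieved with combined tDCS-behavioral therapy but not behavioral therapy alone will persist at 2 weeks, 2 months and 6 months post-intervention".

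Table 1 in section 3b, offered as an example ("an example of which is shown in Table1"), has two sequences: "Group 1: control then sham then tDCS", and the reverse. The text of section 3b puts about 2 months between conditions, and Table 1 has a single 6-month evaluation at the end.

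The plan describes long-term comparison in several ways:
- tDCS methods say the design can "evaluate immediate, short- and long-term effects of each stimulation site without confounds and without any carry-over effects", and then: "We will also conduct a 6-month language evaluation to assess the overall therapy gains".
- The Analyses part of section 3a reports that "the carry-over effect between the first period and the others is small".
- Section 6c assumes that "the effect on the rate of decline persists no longer than 2 weeks", but leaves open whether the effect on the level of the outcome lasts.
- Section 6c analyses change from just before each block, "at follow-up times t=immediately after treatment, then 2 weeks and 2 months". Six months is not among these times.

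Hypothesis 1d predicts an interaction between hemisphere (left or right) and stage (early or middle). tDCS methods assign the left hemisphere to most PPA and all MCI participants, and the right to the most advanced PPA with severe left atrophy. Section 4 excludes advanced stages. Home-based targets (Objectives, section 6a) include right homologs, with no stated allocation by side or stage.

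**The concern.** A claim that benefit lasts with tDCS but not with therapy alone needs a 6-month contrast between the two. By then each sequence has received both, and on an outcome common to both blocks their effects are superimposed. If 1b stays as worded, a 6-month result could be read as lasting superiority over sham when the data cannot tell a lasting gain from a lost one.

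Hypothesis 1d has a parallel problem. If severity largely determines the side stimulated, a left/right difference in response could be read as the predicted interaction when it reflects severity.

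**Working it through.** **Inputs.** Table 1 gives block 1 at W22-24, block 2 at W33-35 (printed W233-35, read as W33-35), and evaluations at W44 and W61. Section 6c gives 30 participants, design effect 1.5, effect size 0.8 and power 75%. Assumed: 1:1 allocation, two-sided alpha 0.05, and effects of the two blocks that add.

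**Lags in weeks.** 33-24 = 9; 44-35 = 9; 44-24 = 20; 61-35 = 26; 61-24 = 37.

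**Notation.** D(k) is the tDCS gain over sham k weeks after a block ends, and m is the level common to both groups at a visit. Group 1 has sham first; Group 2 has tDCS first.

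1. *Six months, shared outcomes.* At W61 Group 1 is at m + D(26) and Group 2 at m + D(37), so the difference is D(26) - D(37). Permanent gain of 1: 1 - 1 = 0. Lost gain: 0 - 0 = 0. Using change from W33 gives D(26) + D(9) - D(37). This is 1 + 1 - 1 = 1 for a permanent gain and 0 + 1 - 0 = 1 for one intact at 9 weeks and gone by 26. A rank check on the two sequence means at all visits after block 1 agrees: D is estimable at lags up to 20 weeks and not at 26 or 37, even if those two are set equal.

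2. *What is identifiable.* D(9) is the W33 difference, Group 2 minus Group 1, before block 2 begins. At W44, Group 1 minus Group 2 is D(9) - D(20). Hence D(20) is the W33 difference minus the W44 difference, if block effects add.

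3. *Planned 2-month change score, shared outcomes.* Block 1 gives D(9). In block 2, Group 1 changes by c + D(9) and Group 2 by c + D(20) - D(9), where c is the common change; the difference is 2D(9) - D(20). The average over the two blocks is [3D(9) - D(20)]/2. Under assumed exponential decay, as fractions of the initial gain:

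| Assumed half-life | D(9) | D(20) | Average | Average / D(9) |
|---|---|---|---|---|
| 8 weeks | 0.459 | 0.177 | 0.599 | 1.31 |
| 21.6 weeks | 0.749 | 0.526 | 0.861 | 1.15 |
| 52 weeks | 0.887 | 0.766 | 0.947 | 1.07 |
| no decay | 1 | 1 | 1 | 1.00 |

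   If D is zero throughout, the average is zero.

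4. *Separate trained sets.* Let T(k) be the therapy gain retained at k weeks. At W61, tDCS-trained minus sham-trained is T(26) - T(37) + D(26) in Group 1 and T(37) - T(26) + D(37) in Group 2. The mean is [D(26) + D(37)]/2: 0.07, 0.37, 0.66 and 1.0 of the initial gain in the table's four cases.

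5. *Power.* The plan's figure reproduces: 30 × 1.5 / 2 = 22.5 per group gives 74.6% by the two-sample t test, against the stated 75%. A first-period comparison of 15 with 15 gives 56.2%.

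6. *Hypothesis 1d.* The interaction is (right middle - left middle) - (right early - left early), which needs four cells. The assignment rule supplies at most early/left, middle/left and middle/right: rank 3 of 4. If the right-stimulated cases fall in the stages section 4 excludes, at most two cells remain. The regression on age and atrophy volume in section 6c does not supply the missing contrast.

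**The case against.** The strongest reply is that no 6-month comparison is planned. tDCS methods give the 6-month visit the purpose of assessing overall gains, and section 6c stops at 2 months. That is correct. A reader might infer from step 1 that the trial will report a badly inflated 6-month effect, but no passage plans that contrast. What stands is that Hypothesis 1b and the claim of long-term effects free of carry-over promise something the design and analysis do not deliver.

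A second reply is that Table 1 is only an example and carry-over is small. The 2-month gap in the text of section 3b already rules out a 6-month value for the first condition before the second begins. None of the three-condition sequences in section 6c ends with sham, so 6 months after sham always follows a later active block. The carry-over assumption in section 6c covers only the rate of decline, while 1b itself asserts benefit beyond the gap.

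Four other strong readings are not supported:
- *Nothing after 2 months can be compared.* Under additivity, 20 weeks can. A gain lost by then would show at W44; a loss between weeks 20 and 26 would not.
- *Untrained items are not measured at 6 months.* The lexical spelling text mentions only two follow-ups, but section 3b tests unpracticed items at the follow-up sessions, which include 6 months. The wording needs aligning.
- *The 2-month test is invalid.* The bias arises only where outcomes are shared across blocks and the effect decays, and it creates no effect where there is none.
- *The early/right cell is certainly empty.* Home-based participants may receive right-sided stimulation with no stated rule by stage. The documents support only that the plan does not provide this group.

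**Conclusion.** The point holds in this form. For outcomes shared across blocks, the 6-month tDCS-versus-sham effect cannot be identified without an assumed decay shape: the W61 difference is zero for both a permanent and a lost gain. That does not depend on the illustrative half-lives or the exact weeks in Table 1. Effects after treatment, at 2 weeks and at 2 months are identifiable, and 20 weeks is too if block effects add. The planned 2-month estimate is 1.07 to 1.31 times D(9) over the assumed half-lives and unbiased without decay.

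Trained items do not escape as a class. Only lexical spelling states a separate trained set for each condition; the phoneme-grapheme, naming and repetition sections do not.

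The interaction in 1d is not identified by the stated assignment and is confounded with severity. The plan's 75% power figure is not in dispute; it covers neither the 6-month contrast nor this interaction.

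**What to change.** 1. Limit the comparative claim in 1b to post-treatment, 2 weeks and 2 months, matching section 6c, with the evaluation before block 2 as the first condition's 2-month point. State that the block-2 change score contains first-block effect. Report the first-period contrast as a sensitivity analysis and, optionally, the 20-week contrast as exploratory with its additivity assumption.
2. Report the 6-month visit as uncontrolled maintenance of the whole programme. Remove the no-carry-over claim for long-term effects. Align the lexical spelling section's two follow-ups with section 3b.
3. Where each condition has its own trained set, pre-specify tDCS-trained versus sham-trained retention at 6 months, adjusted for period and sequence, as a supportive contrast. State that it averages the 26- and 37-week effects and that generalisation between sets dilutes it.
4. Restate 1d as descriptive: tDCS-minus-sham effects by stimulated hemisphere, noting that hemisphere was not randomised and largely follows severity, with no interaction claim.
5. Reconcile the tDCS methods text on the most advanced cases with the exclusion of advanced stages in section 4.

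This costs wording and modest analysis, with no new visits. The downsides are narrower hypotheses, a first-period contrast with only about 56% power, and a trained-set contrast that rests on a subset of participants.

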
Although we do not know the exact mechanisms by which tDCS works, it has been claimed that the low current applied on the scalp has the potential to alter synaptic excitability at the stimulation area (Nitsche et al., 2004; Stagg & Nitsche, 2011). We therefore hypothesize that effects of generalization to other functions will depend on the area stimulated. In the existing literature effects of tDCS in the areas stimulated have been correlated with the cognitive functions subserved by these areas. Furthermore, it has been shown that stimulation of specific areas affects only functions subserved by these areas but not others; Ferrucci and colleagues (2008) have shown that stimulation of the temporo-parietal junction affected word recognition but not visual attention which was subserved by different areas. There is only one other study that has looked at transfer of treatment effects to other language functions. (Marangolo et al., 2011)) have shown that beneficial effects from syllable production training in combination with stimulation at the left inferior frontal gyrus (IFG) of patients with stroke transferred to other production tasks such as word repetition and reading. In the present study we will test the hypothesis that spelling therapy gains will not only generalize to the spelling of untrained items but also to other language and cognitive functions that are subserved by the stimulated areas. In the same logic, we do not expect generalization to language and cognitive functions that have neural substrates different from the stimulated areas.

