# b. Secondary outcome variables.

Secondary outcome variables will be generalization of the improvement induced by the stimulation of IFG and SMG in other language and cognitive functions with the same neural substrates. Therefore improvement may generalize to verbal working memory tasks such as sentence repetition and single digit span backward and forward but will not generalize to functions that do not involve IFG, and SMG, such as picture association.

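### Hypothesis 1c claims that generalisation depends on the site stimulated, but section 6c tests each site only against sham and plans no comparison of IFG with SMG

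*Combined protocol and SAP*

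**What the plan says.** Hypothesis 1c, under Primary Objective 1, states that stimulation during therapy "will improve performance in other language and cognitive functions specific to the region of interest". It then gives two lists. Spelling, naming and working memory are on both. Repetition is listed for SMG only, and articulation and syntactic comprehension for IFG and MTG only.

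The Background (section 2) puts the idea in general terms: "We therefore hypothesize that effects of generalization to other functions will depend on the area stimulated". It adds: "we do not expect generalization to language and cognitive functions that have neural substrates different from the stimulated areas".

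Section 6b makes this a secondary outcome: "Secondary outcome variables will be generalization of the improvement induced by the stimulation of IFG and SMG in other language and cognitive functions" that share the same neural substrates.

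Section 6c gives the test: "Then the research hypothesis that IFG (or SMG) treatment is superior to sham will be tested" by asking whether the distribution of site change minus sham change "is not centered at zero". The null distribution comes from "random permutation of the treatment labels (IFG, S, SMG) of the data for each patient". The only other analysis described there is a regression of tDCS effects on patient characteristics such as age and atrophy volume. No IFG-versus-SMG contrast and no site-by-function interaction appears. MTG is not in the analysis at all.

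**The concern.** To say that a function improves under one site and not under another is to say something about the difference between the sites. Section 6c estimates two other quantities, each site's advantage over sham. Permuting three labels supplies a reference distribution for those statistics; it does not create an IFG-minus-SMG statistic.

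With only these tests to hand, the easy route to a regional conclusion is to note that one site reached significance and the other did not. That compares two p-values rather than two effects. It can produce an apparent site difference when the sites are equally effective, and it can miss a real difference when both reach significance. The regional conclusion is the mechanistic reason for using a second site, so the test that carries it should be fixed before data are seen.

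**Working it through.** **Inputs from section 6c.** 30 participants, design effect 1.5, effect size 0.8, power 75% for one site against sham. The wording of the test is two-sided. Alpha is not stated; 0.05 is assumed.

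**Step 1: reproduce the stated power.** Effective participants: 30 × 1.5 = 45, or 22.5 per arm. Noncentrality: 0.8 × √(22.5/2) = 2.68. Normal approximation: Φ(2.68 − 1.96) = 76.5%; with the noncentral t, 74.6%. The stated 75% is reproduced. The other variants tried do not fit: 15 per arm gives 59% two-sided and 71% one-sided, and 30 per arm gives 87%.

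**Step 2: correlation of the two planned contrasts.** Both subtract the same sham change. With equal variances σ² and equal correlations ρ across conditions, each contrast has variance 2σ²(1 − ρ) and their covariance is σ²(1 − ρ), so their correlation is 0.5. This is an assumption; the plan gives no correlations.

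**Step 3: two equally effective sites, each with 75% power.**
- P(exactly one significant) = 2 × [power − P(both significant)].
- P(both significant) from the bivariate normal with correlation 0.5 is about 0.62.
- 2 × (0.75 − 0.6205) = 25.9%.
- By symmetry, 25.9/2 ≈ 13% falls in each direction.

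A simulated three-condition crossover of 30 patients with within-patient permutation tests (4,000 runs) gave 27% for exactly one significant. A separate simulation of 100,000 trials, calibrated to a paired effect of 0.498, gave 61.6% both significant, 26.5% exactly one and 11.9% neither.

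**Step 4: the direct contrast.** For equal sites an IFG-minus-SMG test rejects in 5% of trials by construction (5.2% in the permutation simulation), or 2.5% in any one direction.

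**Step 5: sensitivity of the two-direction rate.**

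| Varied | Value | Exactly one significant |
|---|---|---|
| Contrast correlation (power 75%) | 0 | 37.5% |
| | 0.25 | 32% |
| | 0.5 | 26% |
| | 0.7 | 20% |
| | 0.8 | 16% |
| Power per site (correlation 0.5) | 50% | 33% |
| | 70% | 29% |
| | 80% | 23% |
| | 90% | 13.5% |

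If neither site works, the rate is 8%.

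**Step 6: what the direct contrast can detect.** With 22.5 effective participants per arm, power is about 75–77% for a true site difference of 0.8 SD, 26–27% for 0.4 SD and about 10% for 0.2 SD.

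**The case against.** Several objections have force.

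- **The plan never states the faulty reading.** A reader might infer that the trial will declare a false site difference a quarter of the time. The documents do not support that. The 26% is the frequency of a significance pattern, and it becomes an error rate only if someone draws the regional conclusion from it. What remains is that Hypothesis 1c has no other specified test.
- **Only half the pattern would support Hypothesis 1c.** For each function on one list only, the hypothesis predicts a direction, and the reverse result would contradict it. The rate of false support is therefore about 13%, to be set against 2.5%. For the three functions on both lists, a one-site result gives the hypothesis no support, so the number of functions named does not simply multiply the risk.
- **Section 6b treats the sites jointly.** It contrasts functions that share the IFG and SMG substrates with functions that involve neither, and it places sentence repetition in the shared group. Site-versus-sham tests can address a claim that each site improves its own list. They do not address the Background's statement that generalisation depends on the area, nor the differing lists in 1c.
- **The second site is conditional.** Section 6c allows for one site only, and both the Analyses text in section 3a and Table 1 show IFG and sham as the only full stimulation periods. The figures apply only where both sites are given.
- **The inputs are borrowed.** The 75% power is not tied to the generalisation outcomes, for which no effect size or SD is given.
- **The direct test is weak for modest differences.** That is a reason to report an interval and limit the claim. Two comparisons with sham do not supply the missing evidence.

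**Conclusion.** The gap is real. The documents make a between-site claim, and section 6c contains no test of it. If significance at one site and not at the other were taken as regional specificity, two equally effective sites would give that pattern in about 26% of trials per function (about 13% in the predicted direction), against 5% and 2.5% for a direct contrast.

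The figures rest on 75% power per site, two-sided alpha 0.05, equal variances and correlations across conditions, no period effect, and all 30 participants receiving both sites. Over contrast correlations from 0.8 to 0 the two-direction rate is about 16% to 37.5%, above 5% throughout.

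A reader might also infer that the comparison of tDCS with sham is undermined. It is not: those tests answer their own question, and the point concerns only the regional conclusion on secondary outcomes. The change should be made, but the main comparison does not depend on it.

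**What to change.** In section 6c, for participants who receive both sites, add the within-patient IFG-minus-SMG contrast, tested by swapping the IFG and SMG labels and reported with its confidence interval. Apply it to each function on which the lists in Hypothesis 1c differ and which is actually measured: repetition, and articulation and syntactic comprehension if they are assessed. Base any statement of regional specificity on that contrast alone. Where only one site is given, or different people receive different sites, report site effects against sham with no specificity claim. State whether MTG is to be analysed, since 1c pairs it with IFG.

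Two of the three orders listed in section 6c give IFG before SMG, so the plan should also say how period is handled in this contrast.

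The cost is small where the data exist: one added contrast, with no change to treatment or sample size. For articulation and syntactic comprehension the data may not exist, because neither the baseline task list in section 3a nor section 6b names a measure of them. The claim becomes harder to reach and the intervals will be wide, with about 26% power for a site difference of 0.4 SD.
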